**Laparoscopic Enclosed Morcellation; Electromechanic Morcellation vs Vaginal
Removal**

Clinical trial registry number: NCT02737553

Document Date: 03/21/2016

Objective

To compare the laparoscopic enclosed electromechanical morcellation and tissue removal thorough vagina with posterior colpotomy in laparoscopic myomectomy procedures.

Background

Laparoscopic tissue removal is one of the most challenging steps for the laparoscopic surgery. Therefore, electromechanical morcellation has long been used to facilitate the tissue removal especially for myomectomy and hysterectomy. However, electromechanical morcellation has undergone increased scrutiny because of important concerns related to tissue dissemination during intracorporeal power morcellation according to the US Food and Drug Administration (FDA) warnings in November 2014.

Design

Prospective randomized interventional clinical study.

Methods

We enrolled 118 patients to the study between 18 to 40 years old with an indication of myomectomy. These indications were infertility, pelvic pain, dysmenorrhea, dyspareunia, and menometrorrhagia. Seventeen patients with prior abdominal surgery and 4 participants without previous vaginal intercourse were excluded from the study. After exclusions, 97 participants randomized into two groups according to sequential randomization; Group 1 (n:49): Enclosed

Electromechanical Morcellation (EEM) and Group 2 (n:48): Vaginal Morcellation (VM).

Statistical Analysis Plan (SAP)

Categorical variables will be analyzed with frequency tables, and descriptive statistics will be calculated for continuous variables. The Shapiro-Wilk normality test will be used to analyze whether continuous data were normally distributed. As the data not normally distributed, Mann-Whitney U test will be used for comparison of two independent groups; Wilcoxon signed rank test will be used to compare two dependent groups. The significance level is taken as 0.05 in all hypothesis tests. All statistical analyses will be performed using the IBM SPSS Version 25.0 statistical package program.

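### Does the undefined term sequential randomization, with nothing said about concealment, call for a change to the plan?

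*Combined protocol and SAP*

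**What the plan says.** The Design section labels the trial "Prospective randomized interventional clinical study". The Methods section reports the flow in the past tense. It starts from "We enrolled 118 patients to the study between 18 to 40 years old with an indication of myomectomy", continues with "Seventeen patients with prior abdominal surgery and 4 participants without previous vaginal intercourse were excluded from the study", and ends with "After exclusions, 97 participants randomized into two groups according to sequential randomization". The arms are Group 1 (enclosed electromechanical morcellation, 49) and "Group 2 (n:48): Vaginal Morcellation (VM)".

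Nothing more is said about allocation. There is no method of generating the sequence, block size, intended ratio, concealment procedure or holder of the list. The SAP section does not mention allocation. It sets out the analysis: "Mann-Whitney U test will be used for comparison of two independent groups", and "The significance level is taken as 0.05 in all hypothesis tests". No blacked-out or missing text is visible at this point in Methods.

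**The concern.** Two separate things are left unsaid.

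- **Generation.** The phrase used for allocation is not a standard term with one meaning. It fits a properly random list worked through in order, and it also fits giving the arms in turn as patients arrive. Only the first is randomization. If the second was used, the Design label would be too strong. The Mann-Whitney p-value would then rest on assuming that successive patients are comparable, which the design would not guarantee.
- **Concealment.** Even a random list can be undone if the person accepting patients can see the next assignment. The Methods section puts 21 exclusions (17 + 4) between enrolment and allocation and does not say whether the next arm was unknown at that step.

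At stake is whether a difference between the arms at the 0.05 level can be credited to the removal technique, or might partly reflect who was steered into which arm.

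**Working it through.** **Inputs, all from Methods unless noted**

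- Enrolled: 118
- Excluded: 17 (prior abdominal surgery) and 4 (no previous vaginal intercourse)
- Randomized: 97, as 49 and 48
- Significance level: 0.05, sidedness not stated (SAP)

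**Step 1. Reproduce the plan's own counts.**

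118 − 17 − 4 = 97, and 49 + 48 = 97. Both agree with the text. Every enrolled patient is accounted for by one of two history-based exclusions or by an assignment. No discretionary refusal after enrolment is reported.

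**Step 2. Does the 49/48 split show how the sequence was made?**

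| Scheme | Chance that the arms differ by exactly one at N = 97 |
|---|---|
| Strict alternation | 1 (exactly 49/48 if Group 1 starts) |
| Permuted blocks of 2, 4, 6 or 8 | 1 (97 leaves a remainder of 1 for each block size) |
| Simple 1:1 randomization | 2 × C(97,48) / 2^97 = 0.161 |

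The split fits all three, so it is no evidence of alternation and no evidence against it.

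**Step 3. How large could the harm be?**

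The documents give no figure for this, so any size is an assumption. Suppose the next arm was fully foreseeable, there is no true difference, and the patients accepted into the two arms differ in mean by 2η standard deviations (+η in one arm, −η in the other). With 49 against 48 patients and a two-sided Mann-Whitney test at 0.05, 40,000 simulated trials per cell give these rejection rates:

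| η | Normal outcome, shift | Exponential outcome, shift | Exponential outcome, scale change with the same mean difference |
|---|---|---|---|
| 0 | 0.05 | 0.05 | 0.05 |
| 0.05 | 0.08 | 0.13 | 0.07 |
| 0.10 | 0.16 | 0.34 | 0.14 |
| 0.15 | 0.30 | 0.60 | 0.24 |

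In the scale-change column, values are multiplied by 1 + η in one arm and 1 − η in the other. For the same mean difference, the rate for a skewed outcome more than halves at η = 0.10 and 0.15 when the selection effect is a change of scale instead of an added constant. The SAP names no outcome, so neither column can be tied to this trial. The first row is the only one that needs no assumption about selection, and there the test holds its level.

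**Step 4. What would a change to the plan alter?**

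The verbs in Methods are past tense: patients were enrolled and excluded, and the 97 are already in two groups of stated size. New wording would record what happened. It would not change an assignment, a group size, a test or a significance level.

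**The case for a change.** The strongest case for acting is that random allocation is the one feature that makes a trial randomized, and the plan's chosen term is unclear on exactly that feature. Brevity explains the omission without filling it. The plan also names no baseline comparison and no covariate adjustment, so nothing else in it would reveal or offset an imbalance. The remedy would cost one or two sentences.

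Much of this stands. A reader of the Methods section cannot tell which meaning applies, and if allocation was by turn, the trial should be described as quasi-randomized when it is reported.

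Two arguments that would make it more than missing detail do not hold.

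- **Inflated error rates.** The rates in Step 3 need a fully foreseeable arm and acceptance that depends on it. Both stated exclusion reasons are matters of patient history and neither suggests exclusion by arm. Since the flow closes at 97, selection could act only before enrolment or through those two criteria. That is possible, but nothing in the text shows it.
- **The p-value has no basis under alternation.** With a random start there are only two possible sequences. Swapping the arms mirrors the Mann-Whitney statistic, so a two-sided p-value based on allocation alone would always be 1. But the SAP does not propose a re-randomization test. The ordinary Mann-Whitney p-value is also valid when the patients in the two arms are exchangeable, which may well hold for patients taken in turn. Alternation would weaken the support for the test without making it wrong.

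**Conclusion.** The gap is genuine, but it is missing detail and not a fault in the design or the analysis. The documents do not show that allocation was non-random, that it was predictable, or that anyone was selected by arm. The plan's counts reproduce exactly, and the 49/48 split cannot separate a random list from alternation. No rule in the plan is shown to produce a wrong result, and no different method of allocation could now be put in its place.

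The size of any effect cannot be given. Under assumed selection the false-positive rate could be anywhere from 5% upwards, depending on an unknown strength and an unnamed outcome, and with no selection it is 5%.

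This conclusion rests on reading the past tense in Methods as meaning that allocation was complete, and on the trial holding a record of how the sequence was made. The method of generation, the holder of the list and any concealment belong in the trial report, as does a quasi-randomized label if the record shows assignment by turn. The plan's tests and significance level stay as they are.

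### The SAP plans no between-arm effect estimate or confidence interval, and no inference at all for categorical outcomes, so the comparison in the Objective has no stated size or precision

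*Combined protocol and SAP*

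**What the plan says.** The Objective is comparative: "To compare the laparoscopic enclosed electromechanical morcellation and tissue removal thorough vagina with posterior colpotomy in laparoscopic myomectomy procedures". It names no outcome, effect measure or margin.

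The Statistical Analysis Plan is one paragraph. On summaries it says: "Categorical variables will be analyzed with frequency tables, and descriptive statistics will be calculated for continuous variables". A normality check follows: "The Shapiro-Wilk normality test will be used to analyze whether continuous data were normally distributed". Then come the tests: "As the data not normally distributed, Mann-Whitney U test will be used for comparison of two independent groups", and "Wilcoxon signed rank test will be used to compare two dependent groups". It closes with the significance level, "The significance level is taken as 0.05 in all hypothesis tests", and the software.

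The paragraph names no difference in means or medians, location shift, risk difference, risk ratio or confidence interval, and neither does the rest of the document.

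**The concern.** A Mann-Whitney test returns a p-value. It does not say by how much the two techniques differ, or which differences the data still allow. Descriptive statistics let a reader subtract one arm from the other, if they are given by arm, but they do not give the uncertainty of that subtraction.

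The gap is wider for categorical variables. The Mann-Whitney sentence follows a check on continuous data, so frequency tables are the whole categorical analysis: no test, no estimate, no interval.

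Two things are at stake. A non-significant continuous result could be taken to mean that the techniques are equivalent, because nothing in the planned output shows which differences remain plausible. And a significant result, or an apparent difference in a table, would be reported without a size and its precision.

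**Working it through.** **Inputs from the document.** Methods: 118 enrolled, 17 and 4 excluded, 97 randomized, 49 to EEM and 48 to VM. Check: 118 − 17 − 4 = 97 and 49 + 48 = 97, so the counts agree. There is no power calculation, SD, event rate or target difference to reproduce.

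**What the plan yields, by type of variable.**

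| Variable type | Summary | Between-arm test | Between-arm estimate | Interval |
|---|---|---|---|---|
| Continuous | descriptive statistics | Mann-Whitney U | none | none |
| Categorical | frequency tables | none | none | none |

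The Wilcoxon signed rank test concerns dependent groups, so it does not fill either row.

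**Illustrative precision.** Assumed, because the document does not give them: two-sided 95% intervals, the shape of the distributions, the event rates, and no true difference between arms.

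*Continuous outcomes.* There are 49 × 48 = 2352 pairwise EEM minus VM differences. The rank cut-off for the Hodges-Lehmann interval is 2352/2 − 1.96 × √(2352 × 98/12) = 1176 − 271.6 ≈ 904, so the interval runs from the 904th smallest to the 904th largest difference.

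- Normal data, large-sample formula: 1.96 × √[(1/49 + 1/48) × π/3] = 0.407 SD. Simulation (8,000 runs): mean half-width 0.414 SD, coverage 0.948.
- Lognormal data, by simulation (6,000 runs each in SD units, 3,000 each in units of the median):

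| Log-SD | Half-width, SD | Half-width, share of median |
|---|---|---|
| 0.25 | 0.391 | 10% |
| 0.5 | 0.327 | 20% |
| 0.75 | 0.246 | 28% |
| 1.0 | 0.165 | 36% |

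Coverage was 0.947 to 0.954. The half-width shrinks in SD units as skewness grows because the SD itself is inflated by the tail; relative to the median it grows.

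*Categorical outcomes.* Expected half-width of the Newcombe interval for the risk difference, by exact binomial enumeration, beside the normal approximation 1.96 × √[p(1 − p)(1/49 + 1/48)]:

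| Common rate p | Newcombe, points | Normal approximation, points |
|---|---|---|
| 5% | 10.5 | 8.7 |
| 10% | 12.8 | 11.9 |
| 20% | 15.8 | 15.9 |
| 30% | 17.6 | 18.2 |
| 50% | 19.0 | 19.9 |

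Newcombe coverage was 0.948 to 0.979.

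*No events in either arm.* With z² = 3.84, the Wilson upper limits are z²/(49 + z²) = 3.84/52.84 = 0.073 for 0/49 and 3.84/51.84 = 0.074 for 0/48. The Newcombe interval for EEM minus VM is therefore −7.4 to +7.3 points. The simple normal-approximation interval has zero width here, and a frequency table would show only two zeros.

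**The case against.** The strongest reply is that nothing planned is wrong. The rank test is valid, the counts add up, and what is missing is reporting that could be added when the results are written. That stands as a limit on severity, but not as an answer: the plan does not promise an estimate, and leaving the measure open lets it be chosen after the data are seen.

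A second reply is that the document names no outcomes, so an added estimate has nothing specific to attach to. It is true that no outcome is named. That is a separate gap, and it means the fix must be worded for whichever outcomes the trial reports. It also means that a categorical variable with more than two levels needs the level of interest named before a risk difference is defined.

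A third reply is that the half-widths do not measure the defect. They follow from the arm sizes and are the same whether or not an interval is printed. This is correct. A reader might infer from them that the trial's conclusions would be overturned, or that the trial is too small. The documents support neither reading: they state no target difference or margin, and every width rests on assumed distributions or rates.

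Finally, the SAP does not say that its tables and summaries will be given by arm. A reader might infer that the arms will not be shown separately at all. In a two-arm comparison, by-arm tabulation is the more reasonable inference, but it remains an inference and the fix should state it.

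**Conclusion.** The omission is real and should be corrected. Continuous outcomes would be compared by a p-value, with descriptive summaries beside it; categorical outcomes would have no between-arm inference.

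It would go too far to say that the plan's tests are invalid, or that the trial claims equivalence. The Objective speaks only of comparing the techniques. The risk is that a null result is read as equivalence, not that the plan proposes to read it so.

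At 49 versus 48, an observed difference of zero could still leave differences of very roughly 0.4 SD plausible for a normal outcome, or about 10 to 19 points for a binary outcome with a common rate of 5% to 50%. The omission itself follows from the text alone. The widths depend on the assumptions listed with the calculations.

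**What to change.** Keep the Mann-Whitney U test, and leave the Wilcoxon signed rank comparisons as they are. Add to the SAP:

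> Each continuous outcome will be compared between arms with the Mann-Whitney U test and reported with the Hodges-Lehmann estimate (median of all pairwise EEM minus VM differences) and its 95% CI; if the two distributions differ clearly in shape, the estimate will be described as the median pairwise difference and not as a shift in location or a difference in medians. Categorical outcomes will be tabulated by arm and compared between arms with the risk difference (EEM minus VM) and its 95% Newcombe CI.

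Other estimates with intervals would also close the gap. Hodges-Lehmann is suggested because it corresponds to the planned rank test, and Newcombe because it still gives a usable interval when an arm has no events.

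The cost is two sentences, one estimate and interval per outcome, and a look at distribution shape. No new data are needed and the Mann-Whitney p-values do not change. The downsides are slightly more output and, when events are rare, intervals somewhat wider than the normal approximation computed from observed rates (expected half-width 10.5 against 8.4 points at a 5% rate).

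### The arms are compared on continuous variables only by an unadjusted Mann-Whitney test; if a pre-operative value of the same variable is recorded, leaving it out costs precision

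*Combined protocol and SAP*

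**What the plan says.** The Objective is a comparison of two techniques: "To compare the laparoscopic enclosed electromechanical morcellation and tissue removal thorough vagina with posterior colpotomy". Under Methods, "97 participants randomized into two groups according to sequential randomization", 49 to EEM and 48 to VM.

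The SAP is a single paragraph. For continuous variables it plans descriptive statistics and a normality check ("The Shapiro-Wilk normality test will be used to analyze whether continuous data were normally distributed"). It then treats the data as non-normal ("As the data not normally distributed") and names two tests, one between groups and one for paired data: "Mann-Whitney U test will be used for comparison of two independent groups; Wilcoxon signed rank test will be used to compare two dependent groups". It names no covariate, regression model or ANCOVA of any kind. It also names no outcome, no baseline measurement and no measurement time.

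**The concern.** In a trial with two parallel randomised arms, a paired test makes sense only if some variable is measured twice on the same patients. The SAP uses that pair only for the paired test, which describes change within patients and does not compare the techniques. The between-arm test, which does address the Objective, uses no earlier value.

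If the earlier value was taken before surgery, randomisation makes it independent of arm, and adjusting for it removes the part of the outcome variance that it explains. The sample is fixed at 97 and the document gives no power calculation, so recorded but unused information is the cheapest source of precision available. At stake is the width of the interval and the chance of detecting a real difference. Bias and type I error are not at stake.

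**Working it through.** **Inputs from the documents.** Arm sizes 49 and 48 (Methods); significance level 0.05 (SAP). Count check: 118 − 17 − 4 = 97, and 49 + 48 = 97. The plan states no power, effect size or SD, so there is no power figure to reproduce.

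**Assumptions, not in the documents.** Two-sided testing, 80% power, and a correlation r between the pre- and post-operative values, taken over the range 0 to 0.7.

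**Step 1: unadjusted comparison, normal scale.**
Detectable difference = (1.960 + 0.8416) × √(1/49 + 1/48) = 2.8016 × 0.2031 = 0.569 SD.
For the Mann-Whitney test on normal data, with efficiency 3/π: 0.569 / √(3/π) = 0.582 SD.

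**Step 2: baseline-adjusted comparison, normal scale.** Adjustment multiplies the variance by 1 − r². The detectable difference is therefore 0.569 × √(1 − r²), and the equivalent unadjusted sample is 97 / (1 − r²).

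| Assumed r | 1 − r² | Detectable difference (SD) | Equivalent unadjusted patients |
|---|---|---|---|
| 0 | 1.00 | 0.569 | 97 |
| 0.3 | 0.91 | 0.543 | 107 |
| 0.5 | 0.75 | 0.493 | 129 |
| 0.7 | 0.51 | 0.406 | 190 |

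Using t quantiles and allowing for the estimated slope, the unadjusted figure is 0.575 SD and the adjusted figures are 0.578, 0.551, 0.500 and 0.413 SD. The pattern is the same, with a trivial loss at r = 0.

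**Step 3: does the gain survive on non-normal data with a rank method?** Simulated power, 49 vs 48, 20,000 runs per cell. The true difference is 0.5 SD, on the log scale for the log-normal and gamma cases and on the underlying normal scale for the score. The four values in each cell are for r = 0 / 0.3 / 0.5 / 0.7.

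| Data | Mann-Whitney | Rank ANCOVA |
|---|---|---|
| Log-normal | 0.663 / 0.662 / 0.661 / 0.657 | 0.659 / 0.694 / 0.766 / 0.895 |
| Gamma, shape 2 | 0.721 / 0.715 / 0.713 / 0.710 | 0.716 / 0.747 / 0.818 / 0.927 |
| 0-10 score, 23% zeros | 0.639 / 0.641 / 0.638 / 0.642 | 0.635 / 0.671 / 0.743 / 0.868 |

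At r = 0, rank ANCOVA loses 0.4 to 0.5 percentage points. At r = 0.3 it gains about 3 points, at r = 0.5 about 10.5, and at r = 0.7 about 22 to 24. Type I error was 0.047 to 0.053 for both methods.

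**Step 4: which scale?** Same simulations, same order of r.

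| Data | Log-scale ANCOVA | Raw-scale ANCOVA |
|---|---|---|
| Log-normal | 0.682 / 0.717 / 0.795 / 0.921 | 0.498 / 0.515 / 0.564 / 0.694 |
| Gamma, shape 2 | 0.689 / 0.721 / 0.794 / 0.916 | 0.779 / 0.806 / 0.871 / 0.960 |

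The log scale is best on log-normal data and weakest of the three ANCOVAs on gamma data. The raw scale does the reverse. Both distributions are skewed and strictly positive, so knowing only that the data are not normal does not pick between them. The rank scale is never the weakest of the three in these cells.

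**Step 5: a readable estimate from the rank model.** Let p be the probability that an EEM value exceeds a VM value, counting ties as half. The EEM-minus-VM difference in mean ranks equals N × (p − 0.5), so p = difference / N + 0.5. Applied to the adjusted difference, this gives an adjusted p. The simulated coverage of its 95% CI was 0.948 to 0.956, with half-width about 0.11 at r = 0 and 0.10 at r = 0.5.

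**The case against.** **The premise is inferred.** The documents name no variable with a pre-operative value. The paired test would also fit two post-operative time points, or could be generic wording. This stands, and it is why the point is conditional. If the earlier value is itself post-operative, it may be affected by the technique and should not be adjusted for.

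**An unadjusted comparison is legitimate.** This also stands. A reader might infer that the Mann-Whitney test is wrong or biased here. It is neither: under randomisation it is valid, and its simulated type I error is near 5%.

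**The size depends on r.** A reader might infer that the plan throws away 32 patients (129 − 97). That figure is the assumed r = 0.5 case, for means on a normal scale. The same sum gives none at r = 0 and 10 at r = 0.3, and nothing in the documents makes one r more likely than another.

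**A specific transformation might seem to follow.** Because the SAP calls the data non-normal, a reader might infer that log-scale ANCOVA should be required and raw-scale ANCOVA ruled out. Step 4 shows that this can choose the weakest option. Non-normal does not mean log-normal.

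**It may be late to pre-specify.** Methods reports enrolment and randomisation in the past tense, and the SAP already calls the data non-normal. The document does not say whether outcomes have been compared by arm. What matters is that the model is fixed before that comparison.

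**Conclusion.** The point holds as a minor, conditional matter of precision. The only planned between-arm method for continuous data ignores any earlier value of the same variable, while the plan itself implies that at least one such value exists. If that value is pre-operative, the detectable difference on a normal scale could fall from 0.57 SD to 0.54, 0.49 or 0.41 SD at r = 0.3, 0.5 or 0.7. The benefit is small at 0.3, material from about 0.5 and nil at 0. These figures assume two-sided 5% testing, 80% power, all 97 patients analysed, and the stated correlations, none of which the documents give. The documents do not support calling this an error of validity, fixing the loss at a particular number of patients, or prescribing a log or raw scale.

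**What to change.** - State in the SAP which continuous variables have a recorded pre-operative value, and name each one before outcomes are compared by arm.
- For each of these, make the between-arm analysis a rank ANCOVA: the ranked post-operative value on arm and the ranked pre-operative value. Do not make this choice depend on the Shapiro-Wilk result.
- Report the p-value and the adjusted mean-rank difference with 95% CI from that one model. Divide the difference and its limits by the number analysed and add 0.5, to give the adjusted probability that an EEM value exceeds a VM value, counting ties as half.
- Keep Mann-Whitney for variables with no pre-operative value. If no variable has one, this change does not apply.
- Say that signed-rank results describe within-arm change and are not a comparison of the arms.

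Cost: SAP wording and one extra model per paired variable. No new data are needed, and the analysis can be run in the package already planned ("All statistical analyses will be performed using the IBM SPSS Version 25.0 statistical package program"). The estimate is on a rank scale, which is less familiar than a difference or a ratio. About half a point of power or less is lost if r is 0. A log or raw scale can be more powerful where its distributional assumption is right, but the documents give no basis for choosing one.

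### Does the unexplained signed-rank test, and the silence on value versus change, leave the comparison of techniques in doubt?

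*Combined protocol and SAP*

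**What the plan says.** The Objective is a comparison between arms: "To compare the laparoscopic enclosed electromechanical morcellation and tissue removal thorough vagina with posterior colpotomy in laparoscopic myomectomy procedures". The Design section reads "Prospective randomized interventional clinical study", and Methods reports "97 participants randomized into two groups according to sequential randomization", with 49 patients in the enclosed electromechanical arm and 48 in the vaginal arm. No matching or crossover is described.

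The SAP is a single paragraph. It justifies rank tests with "As the data not normally distributed" and then assigns two of them: "Mann-Whitney U test will be used for comparison of two independent groups" and "Wilcoxon signed rank test will be used to compare two dependent groups". It adds: "The significance level is taken as 0.05 in all hypothesis tests". It lists no outcomes and no measurement times, and does not say whether anything is recorded before surgery.

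**The concern.** Two things look wrong at first reading.

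- **A paired test in a parallel-group trial.** With two independent arms, a signed-rank test can only assess change within patients. That is not the stated objective, yet the test gets the same 0.05 level as the between-arm test and no stated role. If its p-value were read as evidence about the techniques, it could mislead in both directions: significant when both arms change alike, non-significant when they change in opposite directions.
- **An unstated quantity for the between-arm test.** For an outcome measured twice, comparing arms on one value and comparing them on change are different questions. The same patients can give different answers. If the quantity were chosen after the arm results were seen, the false-positive rate would exceed 5%.

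At stake would be the type I error of the main comparison and the reader's ability to tell which comparison was intended.

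**Working it through.** **1. Are the arms independent?** From Methods: 118 − 17 − 4 = 97 = 49 + 48. The count reproduces, and each patient belongs to one arm. The documents give no effect size, SD, correlation or power, so every input below is an assumption.

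**2. Test against data structure.**

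| SAP test | Structure named | Where it occurs here | Match |
|---|---|---|---|
| Mann-Whitney U | independent samples | 49 v 48 patients | yes |
| Signed-rank | dependent samples | only repeat measurements in the same patients, if any | yes, or idle |

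The comparison of techniques falls to Mann-Whitney U. If nothing is measured twice, the signed-rank sentence has nothing to act on.

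**3. Is Mann-Whitney U valid on either quantity?** Simulation with no true difference, 20,000 replicates per cell, two-sided 5%, correlation r = 0.3, 0.5 and 0.7 between the two times:

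| Data | Follow-up value | Change | Either one significant |
|---|---|---|---|
| Normal | 0.045, 0.048, 0.051 | 0.049, 0.048, 0.053 | 0.084, 0.088, 0.097 |
| Lognormal | 0.051, 0.052, 0.049 | 0.048, 0.051, 0.051 | 0.089, 0.095, 0.094 |

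Each test alone holds 5%. The last column needs someone to run both and report the better one. With two post-operative times and three candidate tests (each time, and change) the figure is 12 to 13%. These are not general upper bounds: they cover one outcome only, and three post-operative times with all pairwise changes gave about 21% at r = 0.5.

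**4. Does one quantity win?** With equal SD at both times, the variance of change is 2(1 − r) times that of a single value. The two are equal at r = 0.5, since 2(1 − 0.5) = 1. Taking Mann-Whitney efficiency as 3/π:

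- SE = √[(1/49 + 1/48)/0.955] = 0.208.
- The difference giving 80% power on the follow-up value is (1.960 + 0.842) × 0.208 = 0.582 SD.
- Power on change is Φ(0.582/[0.208√(2(1 − r))] − 1.960): 66%, 80% and 95% at r = 0.3, 0.5 and 0.7.

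Simulation at 0.5 SD with normal data agrees in pattern: follow-up 66%, 66%, 66%; change 52%, 66%, 86%. The two tests disagree on significance in about 31 to 32% of trials. With a lognormal additive shift both exceed 94% and disagree in 0.3 to 6%. All of this presumes a pre-operative value, which the document does not show. With two post-operative times and the same effect at both, power is 66% at each time and 5% on change, because the effect cancels.

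**5. What if signed-rank results were used to judge the techniques?**

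- Run within each arm, with no true change: the chance that exactly one arm is significant is 2 × 0.05 × 0.95 = 0.095 (simulated 0.0955; 4,000 runs). With the same true change of 0.2, 0.28 or 0.4 SD in both arms it is 38%, 50% and 36%. Mann-Whitney U on change stays at 4.5 to 5.0%.
- Pooled over arms: a shared change of 0.3 or 0.5 SD is significant in 82% or over 99% of trials, against 5% for Mann-Whitney U. With opposite changes of 0.25 SD it is significant in 4%, against 66%.

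These figures show why the signed-rank test cannot stand in for the between-arm test. The SAP does not say that it will.

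**The case for a change.** The best case for a change is that it would cost one sentence. The SAP gives both tests the same level and neither a role. Naming a primary outcome would not by itself settle value versus change. The objective is a comparison, so the reader should be told which quantity carries it. The simulated figures are sound for the inputs assumed.

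The observation itself stands: outcome, times and role are missing, and writing them down would do no harm. The step to a required change does not follow.

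- The sentence may be generic methods wording. No visit or repeated measurement appears anywhere, so the added wording would be a blank template.
- Choosing the follow-up value as default is a trade-off, not a correction: it loses about 20 points of power to change at r = 0.7 and gains about 14 at r = 0.3. Baseline adjustment needs a pre-operative value not shown to be collected.
- Fixing one quantity per outcome holds 5% per outcome only. With two independent outcomes the chance of at least one false positive is still 1 − 0.95² = 9.75%.
- Enrolment and randomisation are reported in the past tense, and the remark on non-normality may mean that data had been examined. If so, a new sentence would be labelling rather than pre-specification.

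**Conclusion.** No change is needed. The plan pairs each test with the right data structure, and the between-arm comparison rests on Mann-Whitney U, which holds about 5% whether applied to a value or to change. An analyst would use Mann-Whitney U for the techniques and read any signed-rank result as a description of change over time. The report should make clear which quantity was compared.

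The size of the issue is conditional. The excess error (8 to 10% with two candidate tests, 12 to 13% with three, for one outcome) requires selection after seeing results. The signed-rank errors require a use that the plan does not propose. The power contrast requires a pre-operative value.

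This conclusion rests on reading the signed-rank sentence as within-patient and secondary to the stated objective. It would change if signed-rank p-values were used to claim that one technique is better, or if the compared quantity were chosen on the results. The absence of a named endpoint is a separate and larger matter, which this point does not settle.
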